Measles, Mumps Rubella (MMR) vaccine is included in immunization schedule so pre-sensitization skin test is not needed as all patients are expected to be immune. In 1989, monovalent measles vaccine was introduced in Nepal for vaccination of infants at age nine months. In 2013, measles-rubella (MR) vaccine was introduced into the national routine immunization schedule and replaced monovalent measles vaccine. The presence of three different antigens in MMR

increases the sensitivity to the injected antigen and decreases the likelihood of anergy. Side effects of MMR include pain during injection, flu-like symptoms, pruritus and burning sensation.

Intralesional (IL) vitamin D is a novel addition to therapies in warts as it is a simple, effective, well-tolerable, and inexpensive method with negligible local and systemic side effects

Side effects of Vitamin D3 include transient mild to moderate pain, edema at the site of injection, resolving within 1 week mild erythema. Further it would be safer to measure serum vitamin D and calcium levels before and after intralesional vitamin D treatment to prevent possible hypervitaminosis D.

Vitamin D3 acts on the principle of immunotherapy by stimulating cell-mediated immunity In addition, it is also claimed to regulate epidermal cell differentiation and proliferation and may modulate cytokine production through its action upon vitamin D receptors(VDRs). VDRs are present in the keratinocytes, melanocytes, fibroblasts, and immune system cells of the skin. Activation of Toll-like receptor (TLR) of human macrophages up-regulates the expression of vitamin D receptor and vitamin D1- hydroxylase genes, leading to induction of the antimicrobial peptide like thymic stromal, lymphopoietin and cathelecidin.  It also reduces the synthesis of IL1a and IL6 resulting in decreased inflammation. VDR activators (VDRAs) have been shown to inhibit cell replication and have immunomodulatory properties.

It is supposed that combining intralesional immunotherapy with a destructive treatment method might enhance the efficacy, shorten the treatment duration, and reduce the possible side effects.

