# **RATIONALE OF THE STUDY**

Intralesional Immunotherapy is a emerging method of treatment of wart in which injection in a single wart causes the resolution of distant warts as well. Compared to other destructive modalities, it is more effective and comfortable for the patient as it obviates the need for individual treatment of each wart. In addition it has a lower rate of recurrence, avoids adverse effects such as scarring, is more cost-effective in multiple warts and decreases the time a physician has to spend on each patient. Further both injection MMR and Vitamin D3 are readily available as compared to other immunotherapeutic agents like PPD and candida antigen.

IL MMR vaccine has been used for a longer time than IL vitamin D and there are more comparative studies showing efficacy of MMR vaccine with rates of clearance ranging from 70.4% to 82.4%. The clearance rates for IL vitamin D ranges from 40% to 90%. As per Committee to Review Adverse Effects of Vaccines; Institute of Medicine (IOE), there is evidence of causal relationship between MMR vaccine and measles inclusion body encephalitis in individuals with demonstrated immunodeficiencies. Hence immunodeficiency is one the exclusion criterias for MMR administration.

The advantages of vitamin D over MMR vaccine are cost-effectiveness, nonrequirement of maintenance of cold chain, easy availability, and feasibility of use in immunosuppressed patients.

As per Institute of Medicine (IOM), the tolerable upper intake of vitamin D is 4000 IU/day for anyone older than 9 years such that annual maximum dose will be 1,460,000 IU. The total amount of vitamin D that we will be administering will be

1,500,000 IU. Furthermore, since we are giving it intralesionally systemic absorption is likely to be low although data on exact amount of IL vitamin D that gets absorbed systemically is not available. In other studies, patients have been evaluated clinically for signs and symptoms of hypervitaminosis D however, no signs of toxicity were observed. 

As per my literature search,

- 1. No previous studies on immunotherapy in wart have been conducted in our country
- No comparative studies have been done to compare IL MMR and IL vitamin D3 in treatment of wart hence we aim to establish efficacy of each and compare the two.

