### Methodology

Based on the computer generated random number table, patients will be assigned to either Group A or Group B once they come to OPD. Informed consent will be taken. After that detailed information of all the patients satisfying inclusion criteria will be recorded in preset pro forma. This will include personal data, past history, medical history, drug history, clinical data like site, size, number, distribution of lesions. History of muscle weakness, bone pain, altered sensorium, anaphylaxis and immunosuppression will also be taken. In patients of group B serum vitamin D level will be measured after 20 days of 3rd dose and 1 month after the last dose to ensure safe monitoring. Photographs of the lesions will be taken before the first treatment session, in every treatment session and 3 months after last session.

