#### **Group B**

All Group B patients will receive a maximum of 0.5 mL Inj. Vitamin D3 (600,000 IU; 15mg/ml) in each session after injection of IL lignocaine with 31 G insulin syringe. In cases of multiple warts, a maximum of 5 warts will be injected at a time. Amount of injection on each wart will depend on the size of each wart. The session will be done at 3 weekly intervals for a maximum of 5 sessions or until complete resolution of warts, whichever is earlier. 

Patient and physician global assessment using 'Visual Analog Scale score' and photographic comparison will be used to assess decrease in size and number of warts and thus the response to treatment. The clinical improvement will rated as complete response, excellent response, good response, poor or no response by the patient and physician global assessment using visual analog scale score at each visit taking baseline clinical photograph as controls. Immediate and late adverse effects of MMR vaccine and Vitamin D will be evaluated after each treatment session. Necessary investigations and intervention will be done if needed. Follow up will be made monthly for three months to detect any recurrence.

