# ANNEXURES

### Department of Dermatology and Venereology

### **BPKIHS**, Dharan

### Proforma for Wart patients

SN:	Group:	OPD/Inpatient no:	Date:			
Name	e					
Age (years): Sex:						
Race/ethnicity:						
Education:		Occupation:				
Address:		Phone no.				
History:						
1) Duration of w	art:	2) Type of wart:				
3) Site	of lesions:	Scalp/Face/Neck/Trunk/Upper	extremities/Lower			
Extremities/Palr	ns/soles/finger/toes					
4) Number of Le	sions at presentatior	1:				
5) Size of lesion:						
6) Progression o	f lesion: Gradual/Rap	bid/Stable/ Regressing				
7) Any associate	d Symptoms:					
	Pruritus: none/ mild,	/ moderate/ severe				
	Pain: none/ mild/ mo	oderate/ severe				
	Burning sensation: n	one/ mild/ moderate/ severe				
8) Associated pe	rsonal Systemic illne	ss: Yes/No				
If yes: HIV/ Diab	etes/ Asthma/ Allerg	ic skin disorders/ Convulsion/ bone	pain/ muscle weakness			
9) Pregnant/ lac	tating mother: Yes/N	Io/ NA				
10) Taking any o	ther drugs: Yes/No					
If yes: Corticoste	eroids/ Immunosupp	ressive/ Others				
11) Past treatme	ent taken: Yes/ No					
If yes: Self-ca	re (Herbs/ Drugs/ Bo	ught from pharmacy)				
Traditio	nal (Traditional beak	ar/Herbalist/Other)				
Fractional (Fractional nealer/ Herbalist/ Other)						
Improve	Seek medical help or treatment (Topical/ Systemic/ Both/ Surgical)					
Timo cin	anent. worse/ NO/ N					
Time Sin						

Reason for treatment:

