# Treatment given: IL MMR/ IL Vitamin D

# Response to treatment

Number	Date	Percentage		Percentage	Side effects	Remarks
of visits		decrease	from	decrease	(nain redness edema Infection scarring	(Vitamin
		haseline		from last visit	ulcer nigmentary changes flu like	
		baseline			symptoms anaphylavis confusion	20 dave
					symptoms, anaphylaxis, comusion,	20 uays
					polyuna, polyupsia, anorexia, nausea,	diter 3
					vomiting, muscle weakness, bone pain,	VISIT, I
					altered sensorium)	month
						after last
						dose)
1 st						
2 nd						
ard						
3.~						
4 th						
5 th						

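### Group B may receive up to 1,500,000 IU of vitamin D in 12 weeks, yet serum calcium is not scheduled and no legible form field records the volume injected

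*Combined protocol and SAP*

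**What the plan says.** The Group B section allows up to 0.5 mL of vitamin D3 per session, every three weeks, for at most five sessions or until the warts clear. Within that cap, "Amount of injection on each wart will depend on the size of each wart". No minimum volume and no rule in mL per unit of wart size is given.

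The Rationale puts the total at 1,500,000 IU. It compares this with a tolerable intake of 4,000 IU/day, "such that annual maximum dose will be 1,460,000 IU". It adds that "systemic absorption is likely to be low although data on exact amount of IL vitamin D that gets absorbed systemically is not available", and that earlier studies, which assessed patients clinically, saw no toxicity.

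On laboratory monitoring, the Methodology states: "In patients of group B serum vitamin D level will be measured after 20 days of" the third dose, with a second measurement one month after the last dose. No baseline sample and no calcium measurement is scheduled. The Introduction, citing an earlier study, remarks that "it would be safer to measure serum vitamin D and calcium levels before and after intralesional vitamin D treatment to prevent possible hypervitaminosis D".

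Beyond these two samples, the Group B section provides that "Necessary investigations and intervention will be done if needed". Item 11 of the Summary leaves withdrawal to the treating physician.

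The proforma has the entry "Treatment given: IL MMR/ IL Vitamin D". The legible columns of its visit table are visit number, date, percentage decrease from baseline and from the last visit, side effects, and remarks. The history page has "5) Size of lesion", recorded at presentation.

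**The concern.** The plan's safety argument for this dose rests on an annual limit that the ceiling slightly exceeds, on an expectation of low absorption for which it has no data, and on earlier studies that looked for clinical signs. With absorption unknown, laboratory monitoring matters more. Symptom checks cannot detect a calcium rise that causes no symptoms. A vitamin D level can do so only indirectly, if a raised value prompts a calcium test, and the plan names no value that should.

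The second part is exposure. The volume varies from patient to patient and is not captured, so the number of sessions gives only an upper bound on cumulative dose. A raised or a normal vitamin D result then cannot be related to what the patient received.

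At stake is the safety monitoring of up to 30 Group B patients. The side-effect objective, per-protocol status and the efficacy comparison do not depend on this point.

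**Working it through.** **Inputs**

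- Group B section: maximum 0.5 mL per session, strength shown as 600,000 IU and 15 mg/mL, three-week interval, at most five sessions.
- Rationale: total 1,500,000 IU; limit 4,000 IU/day.
- Methodology: vitamin D sample 20 days after dose 3 and one month after the last dose.
- Review of Literature: a case report that used 0.1 mL/cm².

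**Reproducing the plan's total.** 1,500,000 / 5 = 300,000 IU per session, which is 0.5 mL × 600,000 IU/mL. The strength is therefore 600,000 IU per mL. Reading it as 600,000 IU per 0.5 mL would give 5 × 600,000 = 3,000,000 IU, which contradicts the stated total.

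**Against the plan's own limit**

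- Annual limit: 4,000 × 365 = 1,460,000 IU. Ratio: 1,500,000 / 1,460,000 = 1.027, or 2.7% above.
- Mean volume at which five sessions reach the limit: 1,460,000 / (5 × 600,000) = 0.487 mL.
- Four full sessions: 4 × 300,000 = 1,200,000 IU, or 82% of the limit.
- Over the dosing period itself: 4,000 × 84 = 336,000 IU; 1,500,000 / 336,000 ≈ 4.5.

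These are injected amounts, not absorbed amounts.

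**Timing.** Doses fall on days 0, 21, 42, 63 and 84. The first sample falls on day 42 + 20 = 62, one day before dose 4. By then up to 3 × 300,000 = 900,000 IU has been given, and up to 2 × 300,000 = 600,000 IU is still to come. With five doses, the second sample falls on about day 84 + 30 = 114, when no session remains to be held.

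**What an unrecorded volume leaves open.** Assume 0.1 to 0.5 mL per session. The low end is the case report's 0.1 mL/cm² applied to 1 cm² of total wart area: one wart of 1 cm², or five warts 5 mm across (5 × π × 0.25² = 0.98 cm²).

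| Recorded sessions | At 0.1 mL each | At 0.5 mL each |
|---|---|---|
| 3 | 180,000 IU | 900,000 IU |
| 5 | 300,000 IU | 1,500,000 IU |

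The same form entries are thus compatible with a fivefold range of dose. Lesion size at presentation does not narrow it, because no rule converts size to volume.

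**The case against.** The plan is not without safeguards. It excludes patients with hypervitaminosis D, bone pain, muscle weakness or altered sensorium, and it takes two vitamin D levels. At each visit the form lists symptoms such as polyuria, polydipsia, vomiting and confusion. Further tests are allowed when needed, and the physician may withdraw a patient. The Introduction's sentence on calcium is a remark from the literature, not a commitment, so leaving calcium out is a choice and not a contradiction. All of this stands. What remains uncovered is the patient with high calcium, no symptoms, and a vitamin D level that prompts nothing. The documents give no rate for that.

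The 1,500,000 IU is a ceiling that the protocol itself discloses, and many patients will receive less. That also stands, but nothing required on the form would show who received how much.

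Recording volume has limited value: absorption is unknown, a clinician can act on a high serum level whatever the dose, and volume could be noted under remarks. This stands in part. Volume is a secondary addition, and without a baseline level it explains a raised result only partly.

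The heading of the remarks column is damaged in the available text, so a lost word cannot be ruled out. What is legible matches the two vitamin D timings in the Methodology, and the Methodology names no other test.

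Finally, a calcium rule can hold a session only on the day-62 result, and only a result back within a day can hold dose 4. This is correct. A slower result can still hold dose 5.

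**Conclusion.** The concern holds. The plan permits up to 1,500,000 IU over 84 days, schedules vitamin D but not calcium, and has no legible field for a volume that varies with wart size. The ceiling is 2.7% above the annual limit that the plan cites. It passes that limit only with five sessions averaging more than 0.487 mL.

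The facts come directly from the documents. The 180,000 to 900,000 IU range for three sessions rests on the assumed 0.1 to 0.5 mL per session. None of these figures estimates the risk of hypercalcaemia, and the documents do not allow such an estimate. This is a gap in safety monitoring that should be closed before the first injection; it does not threaten the trial's comparison.

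**What to change.** 1. Run serum calcium on the two Group B samples already planned: 20 days after dose 3 and one month after the last dose.
2. State in advance which calcium result holds the next session, for example a value above the laboratory's upper reference limit. Arrange for the first result to be back before dose 4 where possible, and otherwise before dose 5. If the vitamin D level itself is meant to trigger action, name that level too.
3. Add a field for volume injected (mL) at each session to the treatment form, and report cumulative IU beside each vitamin D and calcium result.
4. Optional: a baseline vitamin D and calcium sample. It would make later results easier to interpret and help apply the hypervitaminosis D exclusion.

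**Cost.** Items 1 to 3 need one form field and at most 30 × 2 = 60 calcium assays, with no new blood draw. Patients who clear before dose 3 have only the later sample. No assay price is given. If the approximate NRS 60,000 for investigations (Summary, item 16) covers only the 60 planned vitamin D assays, each costs NRS 1,000. If a calcium assay costs 20% to 100% of that, the total is 60 × 200 = NRS 12,000 to 60 × 1,000 = NRS 60,000, or NRS 400 to 2,000 per Group B patient. Both the coverage and the relative price are assumptions. Under Summary item 17 the patient pays, so who bears this cost should be settled. The optional baseline adds one blood draw per Group B patient, plus its assays.

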### Group A

Freeze-dried MMR vaccine single-use vials stored at 2°C–8°C will be reconstituted with 0.5 mL of provided diluent (distilled water) as per manufacturer's instruction immediately before intralesional use. If reconstituted vaccine is not used within 8 hours it must be discarded. All Group A patients will

receive intralesional injection of upto 0.5 mL of reconstituted MMR vaccine into a single or a maximum of 5 warts at a time in case of multiple warts with 31 G insulin syringe with beveled edge facing upward. Amount of injection on each wart will depend on the size of each wart. The intralesional injection will be given every three weeks for a maximum of 5 doses or until complete resolution, whichever is earlier.

#### **Group B**

All Group B patients will receive a maximum of 0.5 mL Inj. Vitamin D3 (600,000 IU; 15mg/ml) in each session after injection of IL lignocaine with 31 G insulin syringe. In cases of multiple warts, a maximum of 5 warts will be injected at a time. Amount of injection on each wart will depend on the size of each wart. The session will be done at 3 weekly intervals for a maximum of 5 sessions or until complete resolution of warts, whichever is earlier. 

Patient and physician global assessment using 'Visual Analog Scale score' and photographic comparison will be used to assess decrease in size and number of warts and thus the response to treatment. The clinical improvement will rated as complete response, excellent response, good response, poor or no response by the patient and physician global assessment using visual analog scale score at each visit taking baseline clinical photograph as controls. Immediate and late adverse effects of MMR vaccine and Vitamin D will be evaluated after each treatment session. Necessary investigations and intervention will be done if needed. Follow up will be made monthly for three months to detect any recurrence.

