# Secondary Objective:

- To determine the clinical and demographic profile of patients with different types of warts visiting Dermatology outpatient department of BPKIHS
- 2. To determine the side effects of IL MMR vaccine and IL Vitamin D in treatment of wart
- 3. To determine Dermatology life quality index (DLQI) in wart patients.

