### Sample size

The study considers a 95% confidence interval, 80% power to estimate sample size. According to the literature review, it was found that 84.6% and 40% improvement were seen with IL MMR and IL Vitamin D respectively.

Now using the sample size estimation formula for 2 proportion

```
Now using the sample size estimation formula for 2 proportion

n = 2p(1-p) (Z\beta + Z\alpha/2)^2
```

n= sample size for each group

 $p_1 = 0.846$ 

 $p_{2} = 0.40$   $p = (p_{1} + p_{2})/2$   $Z_{\alpha/2} = 1.96 \text{ at } 95\% \text{ CI}$   $Z_{\beta} = 0.842 \text{ at } 80\% \text{ power}$ Using above formula, n= 18.54 Considering loss of follow up, sample size in each group= 30 Total sample size= **60** 

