# Follow Up

Number of visits	Date	Percentage decrease from	Recurrence (Yes/No)	Remarks
		baseline		
6 th				
7 th				
8 th				

	छाला रोग जीवनस्तर म	नूल्याङ्रन प्रश्नावली	
दर्ता नंः	मिति	डिएलक्यूआ इस्कोर	
नामः	रोग	ठेगाना.	

यो प्रश्नावली को उद्देश्य गत हप्तामा छालाको समस्या ले गर्दा तपाईको जीवनलाई के कतिको प्रभाव परेको छ भनि \_बुभ्চने हो । कृपया, प्रत्येक प्रश्नमा दिएका जवाफहरुमध्ये जुन उपयुक्त लाग्छ एउटा बॉक्समा \_\_\_]चेन्ह लगाउनुहोस् ।

۹.	गत हप्ता, तपाईको छाला कत्तिको चिलाउने, पोल्ने दुख्ने, वा विभर्ने गरेको थियो ?	धेरै थियो ।	Ť	C)	2
		ठिक्कै थियों।	20. 13		
		अनिकति थियो ।		8	
		पटक्कै थिएन ।		Ì	
ર.	गत हप्ता, तपाईको छालाको समस्याले गर्दा कत्तिको लज्जित वा आफैलाई अप्टेरो रो ने क्षिणो :	धेरै थियो ।			0
	પરવગો પંચા ?	ठिक्कै थियों।			
		अलिकति थियो ।		]	
		पटक्क थिएन ।			
₹.	गत हप्ता, तपाईको खालाले गर्दा किनमेलमा जोंदा, घरायसी काम गर्दा वा वगैचा	धेरै थियो ।	 	ek.	
	जादा कातका अण्ठयारी परका थिया ?	ठिक्कै थियो ।	15 17		
		अलिक ति थियो ।			% 
		पटक्क थिएन ।	1	महत्व थिएन	
8.	गत हप्ता, तपाईको छालाले गर्दा आफनो पहिरनमा कत्तिको प्रभाव परेको थियो ?	धेरै थियो ।	2		3
		ठिक्कै थियो ।			
		अलिकति थियो ।			
		पटक्क ° थिएन ।		महत्व थिएन	
X.	गत इप्ता, तपाईको छालाले गर्दा सामाजिक वा अतिरिक्त कियाकलापमा कत्तिको	धेरै थियो ।	8		2
	असर परेको थियो ?	ठिक्कै थियों।			
		अनिकति थियो ।	30 (		
				महत्व थिएन	
8		पटक्क थिएन ।			
Ę .	गत हप्ता, तपाइंको छालाले गर्दा तपाइंलाई खेलकुद गर्न कत्तिको कठिनाई परेको किन्ने 2	धेरे थियों ।			
	1991.2	ठिक्कै थियो ।	8		
		अनिकति थियो ।		AND	36
		पटक्क थिएन ।		महत्व थिएन	·2
6	गत हप्ता, तपाईको खालाको समस्याले गर्दा आफनो काम वा पढाईमा रोक लागेको	थियो ।			2
	थियो ?	थिएन ।		महत्व थिएन	
20°	यदि "थिएन" भने गत हप्ता तपाईको काम अथवा पढाईमा कत्तिको समस्या आएको	ठिक्कै थियो ।			
	थियो ?	अनिकति थियो ।			
		प्रबद्ध शिएन ।			
80  		and former a			
б.	गत हप्ता, तपाइका छालाका समस्याल गदा तपाइका जामान/जामता, कुनपान नजिकको साथी, अथवा नातेदारसंग कतिको समस्या भएको थियो ?	धरायया ।			
		ठिक्के थियों ।			
		अनिकति थियो ।		गरहर विवास	
		पटक्क थिएन ।		महत्व । थएन	
٩.	गत हप्ता, तपाईको छालाको कारण यौनजन्य समस्या कतिको परेको थियो?	धेरै थियो ।			
		ठिक्कै थियो ।			
		अनिकति थियो ।			
		पटक्क' थिएन ।		महत्व थिएन	
90.	गत हप्ता, तपाईको छालाको उपचारमा कतिको समस्या भोग्नु परेको थियो जस्तै :	धेरै थियो ।	1		
	घर फाहार हुनु अथवा समय वडी लागेको थियों ?	ठिक्कै थियों।			
		अलिकति थियो ।			
		गतका विगाल ।		महत्व थिएन ।	
		नदनक विष्य ।			

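### The side-effects checklist stops at treatment visit 5, so late effects after the fifth dose are not prompted for in either arm, although the plan promises to evaluate them after each session

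*Combined protocol and SAP*

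**What the plan says.** - Methodology, Group B, covers both agents: "Immediate and late adverse effects of MMR vaccine and Vitamin D will be evaluated after each treatment session". Side effects are a secondary objective: "To determine the side effects of IL MMR vaccine and IL Vitamin D in treatment of wart".
- The same section gives follow-up one purpose: "Follow up will be made monthly for three months to detect any recurrence".
- Dosing in Group A is "every three weeks for a maximum of 5 doses or until complete resolution, whichever is earlier". Group B has "3 weekly intervals for a maximum of 5 sessions or until complete resolution of warts, whichever is earlier".
- In the Proforma, the Response to treatment table has a side-effects column with a named list that includes scarring, ulcer, pigmentary change, flu-like symptoms, polyuria, bone pain and altered sensorium. Its rows are visits 1 to 5.
- The Follow Up table (visits 6 to 8) has visit number, date, percentage decrease, recurrence and remarks. It has no side-effects column.
- Methodology also plans photographs three months after the last session for all patients. For Group B it adds a serum vitamin D level "1 month after the last dose to ensure safe monitoring".
- Statistical analysis names chi-square and Fisher's exact tests for categorical comparisons between groups. It does not mention side effects or a window for counting them.

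**The concern.** Late effects of doses 1 to 4 can be entered on the next treatment row, three weeks later. After dose 5 the next scheduled contact is a follow-up visit whose form does not ask about side effects. The text promises late evaluation after every session, and for the fifth session the form gives no prompt for it.

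Two things are at stake. First, side effects in five-dose patients may be under-counted in either arm. In Group B this window follows the highest cumulative vitamin D exposure. Second, because dosing stops at clearance, whether a patient receives a fifth dose depends on the efficacy outcome. Completeness of harm recording could then differ between arms in a comparison that is meant to describe both agents' side effects.

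**Working it through.** **The forms side by side**

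| | Visits 1–5 | Visits 6–8 |
|---|---|---|
| Named side-effects checklist | yes | no |
| Free-text remarks | yes | yes |
| Recurrence | no | yes |

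The gap is plain from the forms. The arithmetic below asks only how large an arm difference it could cause.

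**Inputs from the plan.** Sample size gives the planning rates: "84.6% and 40% improvement were seen with IL MMR and IL Vitamin D respectively". Review of Literature reports these two figures as complete response or clearance. There are 30 patients per arm. The plan's own figure reproduces: p = (0.846 + 0.40)/2 = 0.623, and 2 × 0.623 × 0.377 × (1.96 + 0.842)² / (0.846 − 0.40)² = 18.54 per group.

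**Assumptions, not in the plan.**
- f is the share of eventual clearers who are clear by visit 5, before the fifth dose (range 0 to 1).
- q is the late-effect risk per dose, equal in both arms and independent between doses.
- Late effects of doses 1 to 4 show by the next row.
- Remarks, photographs and the serum level catch nothing after visit 5.
- There is no loss to follow-up.

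**Formulas.** Fifth doses per arm = 30 × (1 − f × clearance rate). A patient is missed only if the sole late effect follows dose 5, so patients missed = fifth doses × q(1 − q)⁴. The multiplier is 0.0407 at q = 5% and 0.0819 at q = 20%. Setting the derivative of q(1 − q)⁴ to zero gives 1 − q = 4q, so q = 20% is the worst case.

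| f | Fifth doses, MMR v vitamin D | Missed at q = 5% | Missed at q = 20% |
|---|---|---|---|
| 1 | 4.6 v 18.0 | 0.2 v 0.7 | 0.4 v 1.5 |
| 0.75 | 11.0 v 21.0 | 0.4 v 0.9 | 0.9 v 1.7 |
| 0.5 | 17.3 v 24.0 | 0.7 v 1.0 | 1.4 v 2.0 |
| 0 | 30 v 30 | 1.2 v 1.2 | 2.5 v 2.5 |

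At f = 1 the arm difference is (18.0 − 4.62) × 0.0407 = 0.5 patients at q = 5%, and 13.38 × 0.0819 = 1.1 at q = 20%. It shrinks to zero as f falls to 0.

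**Other cited rates.** Review of Literature also reports 63% clearance for MMR and 90% for vitamin D. At f = 1 these give 30 × 0.37 = 11.1 v 30 × 0.10 = 3.0 fifth doses. At q = 20% that is 0.9 v 0.2 patients missed, so the direction reverses.

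**Unequal risks.** On the planning rates with f = 1, vitamin D has 18.0/4.62 = 3.9 times as many fifth doses. An MMR per-dose risk more than 3.9 times that of vitamin D would reverse the expected number of unprompted late events.

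**Share of doses.** At f = 1, with clearers spread evenly over one to four doses (mean 2.5, assumed), the share of doses that are fifth doses is 0.154/(0.846 × 2.5 + 0.154 × 5) = 5.3% for MMR and 0.60/(0.40 × 2.5 + 0.60 × 5) = 15.0% for vitamin D. The ceiling is 20% in either arm (f = 0). These shares look larger than the patient-level effect because a patient already counted after doses 1 to 4 loses nothing.

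**The case against.** The strongest reply is that this is one missing column on an annexed form.

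- **Partial capture exists.** Visits 6 to 8 have remarks. The 3-month photographs can show scarring, ulceration and pigmentary change in both arms. Group B has a serum level after the last dose, and the treatment table's remarks heading reserves a place for it. This stands, so it would be wrong to say there is nowhere to record a late effect. But free text is not a checklist, photographs do not show systemic symptoms, and a serum level does not record symptoms and is taken in one arm only.
- **The form does not say that effects of one dose go on the next row.** Row 5 could hold later effects of session 5. That is possible, but no scheduled contact before visit 6 would supply the information.
- **Prompted time is not simply shorter in non-clearers.** A five-dose patient is prompted from week 0 to week 12. The plan does not say whether a patient who clears early still attends the remaining treatment rows. Earlier doses are covered for about three weeks, in a cell shared with the next dose's immediate effects. This stands too.

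A reader might infer that harms will be under-counted most in the arm that clears fewer patients, and that this arm is vitamin D. The documents do not support that as a fact. It needs clearance before dose 5, similar per-dose risks in two different agents, and little capture by other routes. Which arm it would be depends on the pair of clearance rates chosen. Nor can 15% and 60% be read as minimum shares receiving five doses. They ignore loss to follow-up, for which the plan raises 18.54 to 30 per group, an implied allowance of (30 − 18.54)/30 = 38%.

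**Conclusion.** The inconsistency between text and form is real. Late effects of the fifth dose, and effects of earlier doses first appearing after visit 5, are not prompted for in either arm. Under the stated assumptions this costs between 0.2 and 2.5 patients of 30 in an arm on the planning rates, for q of 5% to 20%. Effects of earlier doses that surface after visit 5 would add to this, and capture by remarks, photographs or the serum level would reduce it.

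A difference between arms is possible but conditional. On the planning rates it is about one patient or fewer of 30 (1.1 at most, or 3.7 percentage points), and its direction is not established. The case for change rests on the gap in collection, which affects a stated secondary objective, and not on a demonstrated bias. It should be corrected because correction is nearly free.

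**What to change.** 1. Put the visit 1 to 5 side-effects checklist on the visit 6 to 8 form in both arms, and add adverse effects to the stated purpose of follow-up.
2. Count adverse events from first dose through the one-month visit after each patient's last dose (visit 6 for a five-dose patient). Say what late means, and from when the monthly visits run for patients who stop early.
3. Report side effects by patient, together with the number of doses received. The window in step 2 still lengthens with doses given, so it does not remove the dependence on clearance. Showing doses lets the reader allow for it.

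The cost is one extra form column and a few sentences in Methodology and Statistical analysis. The three monthly visits are already planned. Reported side-effect rates may come out slightly higher.
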